### 10.5.1 Demography and Baseline Characteristics

Demographic and baseline characteristics will be summarized descriptively by treatment group. Continuous variables will be summarized with mean, median, SD, minimum, and maximum. Categorical variables will be summarized with frequency and percentage.

## 10.5.2 Safety Analysis

The primary objective of this study is to evaluate the safety and tolerability of 400mg dose of bermekimab. Safety endpoints will be evaluated by monitoring adverse events from clinical and laboratory reporting. The safety analysis will be based on the SAF population defined as all subject who received at least one dose of study medication. A summary of safety results will be presented for each treatment group.

### 10.5.2.1 Analysis of Adverse Events

Adverse events reported in this study will be coded using the Medical Dictionary for Regulatory Activities (MedDRA) coding dictionary (version 21.0 or newer). Coding will be to lowest level terms. The verbatim text, the PT, and the primary SOC will be listed in patient listings.

Pre-treatment AEs are defined as those that develop or worsen in severity from the time the patient provides informed consent, prior to the first dose of study drug. Treatment emergent AEs (TEAEs) are defined as AEs that develop or worsen in severity following the first dose of study drug through the last study visit.

TEAEs will be grouped by MedDRA System Organ Class (SOC) and Preferred Term (PT) within SOC and will be presented for each treatment group. The number and percent of subjects reporting at least one adverse event by PT will be summarized across groups A & B. The number and percentage of patients experiencing AEs and TEAEs will be summarized by seriousness (SAEs), severity (grades 1-5), SOC, and PT.

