## 5. TREATMENT PLAN

### 5.1 STUDY PROCEDURES

**Screening (maximum 21 days):** The screening period begins once the informed consent is signed.

- Informed Consent
- Demographics
- Medical History
- Concomitant Medications
- Physical Exam
- Vital Signs (blood pressure, pulse, oxygen saturation, respiratory rate and body temperature)
- Height
- Weight
- Body Mass Index (BMI) [BMI= weight (kg)/height (m^2)]
- Blood Draw:
  - Chemistry panel: Albumin, Alkaline Phosphatase, ALT, AST, GGT, Bicarbonate (CO2), Calcium, Chloride, Creatinine, Glucose, Potassium, Sodium, Total Bilirubin, Total Protein, Urea Nitrogen
  - Hematology Panel: Complete Blood Count (CBC) with differential and platelets
  - Infectious disease screening: HIV antibody, Hepatitis C antibody, Hepatitis B panel (HBsAg, anti-HBc, anti-HBs), and interferon gamma release assay (IGRA)
  - Serum pregnancy test for WOCBP
  - Inflammation Markers: CRP (C-Reactive Protein), ESR (Erythrocyte Sedimentation Rate)

Visit 1 (day 0, must occur within 21 days of signing informed consent):

- ***At least 45 minutes before injection:*** Remove syringe from refrigeration and lay flat; allow to warm to room temperature. Do not heat
- Pre-injection
  - Physical Exam
  - DLQI

- Urine pregnancy
- HISCR
- PGA
- Disease Activity Score
- Modified Sartorius
- HADS
- VAS for disease
- VAS for pain
- Vital signs (blood pressure, pulse, oxygen saturation, respiratory rate and body temperature)
- Blood draw for PK and biomarker analysis
- Bermekimab subcutaneous injection, in accordance with injection site determined by BMI at Screening
- 1 hour monitoring for injection reaction
- Vital signs (blood pressure, pulse, oxygen saturation, respiratory rate and body temperature) one hour post injection (70 +/- 10 minutes)
- Adverse event monitoring
- Concomitant medications/treatments

Visit 2 (day 7 +/-2):

- ***At least 45 minutes before injection:*** Remove syringe from refrigeration and lay flat; allow to warm to room temperature. Do not heat
- Pre-injection
  - Urine pregnancy
  - Vital signs (blood pressure, pulse, oxygen saturation, respiratory rate and body temperature)
- Bermekimab subcutaneous injection, in accordance with injection site determined by BMI at Screening
- 1 hour monitoring for injection reaction
- Vital signs (blood pressure, pulse, oxygen saturation, respiratory rate and body temperature) one hour post injection (70 +/- 10 minutes)
- Adverse event monitoring

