## 5.2 STUDY CALENDAR

Visit	Screen	1	2	3	4	5	6	7	8	9	10	11	12	13	14
Study Day		0 ± 2	7 ± 2	14 ± 2	21 ± 2	28 ± 2	35 ± 2	42 ± 2	49 ± 2	56 ± 2	63 ± 2	70 ± 2	77 ± 2	84 ± 2	91 ± 2
Informed Consent	x														
Demographics	x														
Medical/ Surgical History	x														
Infectious Disease Panel+ (part of blood draw)	x														
Serum Pregnancy (part of blood draw)	x														
Height, Weight, Body Mass Index (BMI)	x														
Vital Signs △	x	x	x	x	x	x	x	x	x	x	x	x	x	x	x
Urine Pregnancy		x	x	x	x	x	x	x	x	x	x	x	x	x	x
PK & Biomarker Blood Draw		x		x		x				x					x
Bermekimab Injection♦		x	x	x	x	x	x	x	x	x	x	x	x	x	x
DLQI		x		x		x		x		x		x		x	x
HADS		x		x		x		x		x		x		x	x
Physical Exam	x	x		x		x		x		x		x		x	x
Lab Blood Draw a,b,c	x		x		x					x				x	
HiSCR		x		x		x		x		x		x		x	x
PGA		x		x		x		x		x		x		x	x
Disease Activity Score		x		x		x		x		x		x		x	x
Modified Sartorius		x		x		x		x		x		x		x	x
VAS for disease		x		x		x		x		x		x		x	x
VAS for pain		x		x		x		x		x		x		x	x
Adverse Events		x	x	x	x	x	x	x	x	x	x	x	x	x	x
Concomitant Medications*	x	x	x	x	x	x	x	x	x	x	x	x	x	x	x

aChemistry Panel including: Albumin, Alkaline Phosphatase, ALT, AST, GGT, Bicarbonate (CO2) Calcium, Chloride, Creatinine, Glucose, Potassium, Sodium, Total Bilirubin, Total Protein, Urea Nitrogen

bHematology Panel including: Complete whole blood (WBC, HgB, Platelet, differential)

c CRP (C-Reactive Protein) and ESR (Erythrocyte Sedimentation Rate)

+ HIV antibody, Hepatitis C antibody, Hepatitis B panel (HBsAg, anti-HBc, anti-HBs), and interferon gamma release assay (IGRA)

△ Vital signs include blood pressure, pulse, oxygen saturation, respiratory rate and body temperature

♦ Each bermekimab injection will be followed by 1 hour monitoring for injection site reaction and vital signs 1 hour post injection (70+- 10 minutes)

\* Concomitant medications within 30 days before screening until 7 days after the last administration of the study drug must be recorded for the purpose of drug-drug and drug-disease interaction evaluation and signal detection.

**BMI:** Body Mass Index [BMI= weight (kg)/height (m^2)]

**DQLI:** Dermatology Quality of Life Index

**HiSCR:** Hidradenitis Suppurativa Clinical Response Score

**PGA:** Physicians' Global Assessment

**VAS:** Visual Analogue Scale

**HADS:** Hospital Anxiety Depression Scale

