## 7. ASSESSMENT OF SAFETY

Safety will be assessed by monitoring adverse events, vital signs, physical examinations, and clinical laboratory measurements. All subjects will be included in the safety analysis. Adverse events will be monitored from visit 1 (post-injection) through visit 14. Any serious adverse events or grade 2 or greater probably or definitely related events will be followed up until resolution.

Study drug will be administered under close observation in a facility equipped to handle anaphylaxis. Subjects must be closely monitored until at least 1 hour following the administration of the antibody or 1 hour after their vital signs have stabilized.

Any AE (with the exception of worsening HS symptoms or injection site reactions) of grade 2 or higher must be reported to the sponsor within 24 hours of learning of the event. Any grade 3 or greater injection site reaction must be reported to the sponsor within 24 hours of learning of the event.

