## **9.3 RECORDING OF ADVERSE EVENTS**

All untoward events occurring between visit 1 and visit 14 (or if subject terminates from study prior to visit 14, seven days after the last administration of bermekimab) on the eCRF, regardless of whether they are considered related to study drug.

All AEs should be recorded in a standard medical terminology as concisely as possible. The AE recorded should not be a procedure or a clinical/laboratory measurement but should reflect the event leading to the procedure or the cause of the clinical/laboratory abnormality, if known. Whenever possible, AEs should be evaluated and recorded as a diagnosis, rather than individual signs and symptoms. However, if a definitive diagnosis is not possible, the individual signs and symptoms should be recorded. Any AE that worsens in intensity, or becomes serious, should be recorded as a new event.

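### Section 10.5.2.1 defines pre-treatment adverse events from consent, but collection starts at visit 1, so that category will be empty or nearly so

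*Combined protocol and SAP*

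**What the plan says.** Section 10.5.2.1 divides adverse events in two. The pre-treatment class runs from consent to the first dose: "Pre-treatment AEs are defined as those that develop or worsen in severity from the time the patient provides informed consent". The second class begins with dosing: "Treatment emergent AEs (TEAEs) are defined as AEs that develop or worsen in severity following the first dose of study drug". The planned tables cover both: "The number and percentage of patients experiencing AEs and TEAEs will be summarized by seriousness (SAEs), severity (grades 1-5), SOC, and PT".

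The collection rules sit elsewhere in the same document. Section 7 states: "Adverse events will be monitored from visit 1 (post-injection) through visit 14". Section 9.3 gives the recording window as "All untoward events occurring between visit 1 and visit 14". In the Section 5.2 calendar, the row "Adverse Events" is marked at visits 1 to 14 and is blank at Screening, whereas the concomitant medication row is marked there. Section 5.1 lists no AE item among the screening procedures, although it says "The screening period begins once the informed consent is signed". It also says that visit 1 "must occur within 21 days of signing informed consent".

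**The concern.** The analysis section defines a class of events that the data collection sections do not gather. Safety and tolerability is the primary endpoint, so this touches the main output of the study.

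Three things are at stake. First, a defined category would have almost nothing in it, and two tables meant to differ would be nearly the same. Second, serious events between consent and first dose might not be recorded. Third, the TEAE rule relies on worsening after the first dose, which can be judged only against a grade from before that dose. For some conditions the plan requires no such grade.

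**Working it through.** The plan gives no figure of its own here, so the check is to set the sections side by side, followed by short arithmetic.

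**1. Start of the window**

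| Source | AE window starts |
|---|---|
| Section 10.5.2.1, pre-treatment AEs | Informed consent |
| Section 7 | Visit 1, after the injection |
| Section 9.3 | Visit 1, before or after injection not stated |
| Section 5.2 calendar | Visit 1 (14 marks; Screening blank) |
| Section 5.1 screening list | No AE item |
| Section 9.6, serious AEs | No start date given |

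Only Section 10.5.2.1 begins at consent. Section 9.3, on its widest reading, adds the pre-injection hours of visit 1. The pre-treatment class is therefore empty or nearly so.

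**2. Length of the gap**

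- Longest interval from consent to first dose: 21 days (Section 5.1).
- Visit 1 to visit 14: day 0 to day 91 (Section 5.2).
- Participation: 21 + 91 = 112 days = 16 weeks, which agrees with the synopsis (3 weeks of screening plus 13 of treatment).
- Share with no planned AE collection: 21/112 = 18.75% at most.

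**3. What happens to an event that starts in screening**

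- It resolves before the first dose: it is lost from the record but does not enter the TEAE table.
- It starts before the medical history is taken: the history can hold it.
- It starts after the history and is still present at first dose: no AE entry, onset or grade is required before dosing. The visit 1 pre-injection examination, vital signs and disease scores may reveal it, but they need not grade a symptom such as a headache. Section 9.3 has a worsening AE entered as a new event, which presumes an earlier entry.
- It is a laboratory change after the screening sample: neither Section 5.1 nor the calendar lists a chemistry or hematology draw at visit 1, so it first appears after dosing has begun. Section 10.5.2.2 nevertheless tabulates laboratory change from baseline and laboratory AEs of grade 2 or higher, and Section 8.1 sets baseline at visit 1 before the injection.

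Only the last two routes can lead to misclassification.

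**4. Weight of one misclassified patient**

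- All patients: 1/20 = 5 percentage points.
- Within Group A or Group B: 1/10 = 10 percentage points.

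**The case against.** The strongest reply is that this is a wording mismatch with little effect. The TEAE definition already excludes an event known to predate dosing that has not worsened. Section 9.5 obliges the investigator to weigh timing relative to dosing, which presupposes a known onset, and the eCRF may record an onset date. Visit 1 has a pre-injection examination, and concomitant medications are recorded from 30 days before screening, so a treated condition leaves a trace. The safety analysis is descriptive, with no test to distort, and events after dosing are collected in full. Deleting the pre-treatment definition would also remove the mismatch.

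Most of this stands, and it rules out stronger readings that a reader might infer:

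- That pre-treatment AEs cannot exist. Section 9.3 does not bar an event at visit 1 before the injection.
- That screening events in general cannot be told apart from TEAEs. Events that resolve before dosing never reach the table, and known onset settles many others.
- That severity before dosing is never recorded. The visit 1 assessments supply part of it.
- That serious events in screening go entirely unrecorded. Section 9.6 asks for all of them and sets no start date, so capture is uncertain rather than excluded.

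Nor do the documents give an AE rate for the screening period, so they support no count of lost events.

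Two parts of the reply do not hold. An onset date, if collected, does not supply a grade before dosing, and worsening turns on grade. Also, the error need not only inflate TEAEs: without an earlier grade, a real worsening could be set aside as pre-existing. Deleting the definition would restore consistency, but on its own would leave conditions ongoing at first dose ungraded.

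**Conclusion.** The inconsistency is real and should be corrected. As written, a defined part of the primary safety analysis will be empty or nearly so, the AE and TEAE summaries will be almost identical, and up to 21 of 112 days per patient have no planned AE collection. Capture of serious events in screening is not assured.

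The effect on TEAEs is narrow, and most are unaffected. The exposure is confined to conditions that begin after the screening history, persist at first dose and are not graded at the visit 1 pre-injection assessments, and to laboratory changes after the screening sample. How many patients this involves cannot be estimated from the documents. Because the study is small and uncontrolled, one such patient moves an incidence by 5 points overall or 10 within a group.

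The 21-day figure is the permitted maximum. Actual screening may be shorter, and the window need not apply to patients who move from 200 mg to 400 mg at their next visit under Section 5.5. The 5- and 10-point figures assume the planned 20 patients, 10 per group, all in the safety set.

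**What to change.** Align Sections 5.1, 5.2, 7 and 9.3 with Section 10.5.2.1:

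- Start collection of AEs and serious AEs at informed consent in Sections 7 and 9.3, and state the same start in Section 9.6.
- Add an AE item to the screening list in Section 5.1 and mark Screening in the calendar AE row.
- At visit 1, before the injection, record each ongoing event with its onset date and grade.
- Keep the TEAE definition as it stands.

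This does not settle the laboratory part. Section 10.5.2.2 should also say which sample serves as laboratory baseline, given that none is listed at visit 1.

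The cost is a wording amendment and a small amount of extra data entry at screening and visit 1. Events not recorded during screening cannot be reliably reconstructed later.

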### 10.5.2.2 Other Safety

#### Vital Signs

Summaries of vital sign parameters by treatment dose cohort will include:

- Each vital sign parameter (blood pressure, pulse, oxygen saturation, respiratory rate and body temperature) and change from baseline
- The number (n) and percentage (%) of patients with grade 2 or greater vital sign AEs
- Listings will be provided with flags indicating the AE grade

#### Laboratory Tests

Clinical laboratory values will be converted to standard international units. Clinical laboratory (hematology and chemistry) data will be listed for each subject. Laboratory data will be summarized by treatment group. Values outside the normal reference range will be flagged as high or low on the listings. Summaries of

laboratory variables by treatment group will include:

- Each laboratory result and change from baseline
- The number (n) and percentage (%) of patients with grade 2 or greater laboratory AEs

#### **10.5.3 Analysis of Secondary Endpoints:**

Proportion of patients achieving a positive Hidradenitis Suppurativa Clinical Response (HiSCR) score after 13 weeks will be summarized by treatment group (and pooled overall population). The corresponding 95% confidence interval (CI) for the point estimate will be provided. Subjects previously enrolled in the 200mg/weekly dosing cohort who have received *two or fewer* bermekimab injections (2 x 200mg doses) before beginning the 400mg weekly doses will be included for data analysis together with those receiving all doses at 400mg/weekly. Patients who have received more than 2 bermekimab injections of 200mg may enter the 400mg/week arm; however, only patients who have received *two or fewer* bermekimab injections will be included in the data analysis.

Change in outcomes from baseline to week 13 (VAS for disease, VAS for pain, DLQI, inflammatory lesion count, PGA, Disease Activity Score, and modified Sartorius score) will be summarized using descriptive statistics (n, mean, standard deviation, median, minimum and maximum value). The 95% CI of the mean change from baseline will be provided.

A rank-ordered analysis will be performed for the total abscess and inflammatory nodule count (ranked at 0, 1 or 2) and reduction in pain score (categorized as  $\geq 30\%$  reduction on pain score among patients with baseline score of  $\geq 3$ ). The change in modified Sartorius score will be dichotomized at 4 ( $\leq 4$  least severe disease, higher indicates severe disease). Number and percent under each treatment group (and pooled overall) will be summarized.

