## **3. STUDY DESIGN AND OBJECTIVES**

Phase 2, Open label, multicenter study of two dose cohorts of bermekimab in patients naïve to or having failed prior anti-TNF therapy with moderate to severe Hidradenitis Suppurativa. Bermekimab administered subcutaneously at a dose of 400 mg weekly (13 doses). Patients will be followed for 13 weeks to allow for assessment of safety and preliminary efficacy.

The study protocol will be approved by the Institutional Review Board (IRB) or the Ethics Committee (EC) of the participating study sites. Depending on the participating countries both local and central IRB/EC approvals will be granted. The study will be registered at [www.clinicaltrials.gov](http://www.clinicaltrials.gov) before the enrollment of the first patient. The trial will be conducted in compliance with the protocol, GCP, and all applicable regulatory requirements.

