#### ***Secondary Endpoints:***

- Hidradenitis Suppurativa Clinical Response (HiSCR) from baseline (visit 1) to visit 13.
- Assessment of Pharmacokinetics (PK)
- Change in patient reported outcomes from baseline (visit 1) to visit 13 (VAS for disease, VAS for pain, DLQI).
- Change in Physician's Global Assessment (PGA), Disease Activity Score, and modified Sartorius score from baseline (visit 1) to visit 13.
- Change in inflammatory lesion (abscesses and inflammatory nodules) count from baseline (visit 1) to visit 13.
- Change from baseline (visit 1) to visit 13 in Hospital Anxiety Depression Scale (HADS).

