## 4. ELIGIBILITY CRITERIA

### 4.1 INCLUSION CRITERIA

**No waivers/exemptions will be granted for protocol inclusion/exclusion criteria.**

Subjects are included in the study if they meet all of the following criteria:

- Written informed consent provided by the patient.
- Male or female, age  $\geq 18$  years.
- For group A, patients must have received and failed anti-TNF therapy. For group B, subjects must not have received any prior treatment with any anti-TNF therapy.
- Patients who have received 200mg dose of bermekimab in this study are eligible to begin receiving 400mg dose starting with the patient's next scheduled visit for the remainder of his/her treatment plan.
- Diagnosis of HS for at least 1 year prior to screening.
- HS affecting at least two distinct anatomic areas, one of which is Hurley II or III stage.
- A total body count of abscesses and inflammatory nodules (AN) of at least 3
- Full understanding of the procedures of the study protocol and willingness to comply with them.
- In case of female patients of childbearing potential, willingness to use one method of contraception of high efficacy during the entire study period. This method can be hormonal contraceptives or one of the following: condoms, diaphragm, or an intrauterine device. Women of non-childbearing potential include those considered to have a medical history that indicates that pregnancy is not a reasonable risk, including post-menopausal women and those with a history of hysterectomy.

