are more than 5 abscesses or draining fistulas. The PGA will be measured on visits 1, 3, 5, 7, 9, 11, 13 and 14.

- Disease Activity Score (baseline to visit 13). This is defined as the sum of scores of all affected areas of each patient. Each area will be evaluated by the following formula: (multiplication of the two largest diameters in each affected area in mm) x (the degree of inflammation of each lesion). This score has been proposed by our study group. The Disease Activity Score will be measured on visits 1, 3, 5, 7, 9, 11, 13 and 14.
- The modified Sartorius score (baseline to visit 13). The Sartorius Scale is used to quantify the severity of HS. Points are awarded for 12 body areas (left and right axillae, left and right sub/inframammary areas, intermammary area, left and right buttocks, left and right inguino-crural folds, perianal area, perineal area, and other): points were awarded for nodules (2 points for each); abscesses (4 points); fistulas (4 points); scars (1 point); other findings (1 point); and longest distance between two lesions (2-6 points, 0 if no lesions); and if lesions are separated by normal skin (yes-0 points; no-6 points). The total Sartorius score is the sum of the 12 regional scores. The modified Sartorius score will be measured on visits 1, 3, 5, 7, 9, 11, 13 and 14.
- Change in AN count (baseline to visit 13). The sum of abscesses and inflammatory nodules for each patient will be measured on visits 1, 3, 5, 7, 9, 11, 13 and 14.
- Change in VAS for Disease Severity and Pain (baseline to visit 13). Patient reported visual analogue scales for pain and disease severity will be measured on visits 1, 3, 5, 7, 9, 11, 13 and 14.
- Change in Dermatology Life Quality Index (DLQI) (baseline to visit 13). This will be measured on visits 1, 3, 5, 7, 9, 11, 13 and 14.
- Change in Hospital Anxiety Depression Scale (HADS) (baseline to visit 13). This will be measured on visits 1, 3, 5, 7, 9, 11, 13 and 14.

Changes in secondary endpoints will be presented by individual cohort, as well as combined across both cohorts.

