## 10.3 Analysis Sets

### 10.3.1 Safety Analysis Sets

The safety analysis set (SAF) consists of all patients that receive at least one dose of study medication and will be analyzed as treated.

The secondary endpoints will be analyzed based upon the SAF, as well as the per protocol population (PP). The per protocol population will consist of those patients that complete both the baseline (visit 1) and visit 13 assessments of their hidradenitis (HISCR, PGA, Modified Sartorius, VAS, and DLQI).

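### Sections 10.3.1 and 10.5.3 give different secondary-endpoint populations for patients with more than two 200 mg injections, and the safety, exposure and PK summaries have no rule separating 200 mg from 400 mg data

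*Combined protocol and SAP*

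**What the plan says.** **Crossover.** Section 4.1 makes patients already given 200 mg in this study "eligible to begin receiving 400mg dose starting with the patient's next scheduled visit". Section 5.5 requires that 200 mg and 400 mg injections together total 13. Neither section caps the 200 mg share, and 10.5.3 provides for the larger shares: "Patients who have received more than 2 bermekimab injections of 200mg may enter the 400mg/week arm".

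**Secondary endpoints.** Section 10.3.1 states: "The secondary endpoints will be analyzed based upon the SAF, as well as the per protocol population (PP"). The SAF is everyone with "at least one dose of study medication and will be analyzed as treated". The PP set needs only completed visit 1 and visit 13 assessments. Section 10.5.3 pools patients who had two or fewer 200 mg injections with the all-400 mg patients, and says that only patients with two or fewer "bermekimab injections will be included in the data analysis". It names no analysis set. PK is a listed secondary endpoint, but is analysed under 10.5.4 as an average concentration by visit.

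**Safety and exposure.** Sections 8.2 and 10.5.2 set the primary endpoint and objective as safety and tolerability at 400 mg. Section 7 puts all subjects in the safety analysis. Section 10.5.2.1 counts treatment-emergent events from the first dose of study drug, and 10.5.5 counts exposure from the first injection.

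**Grouping terms.** Section 3 describes a "multicenter study of two dose cohorts of bermekimab" but gives one dose. Section 8.2 says: "Changes in secondary endpoints will be presented by individual cohort, as well as combined across both cohorts". Vital signs (10.5.2.2) are summarised by *treatment dose cohort*, laboratory data by *treatment group*, and dose number and volume (10.5.5) by *treatment arm*. Section 10.5.3 also uses *dosing cohort* for the 200 mg patients. None of these terms is defined for a patient who received both doses.

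**The concern.** There are two separate problems.

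First, a patient with three or more 200 mg injections is in the secondary-endpoint population under 10.3.1 and out under 10.5.3. Two analysts could each follow the plan and report different denominators. With planned groups of 10, a few patients either way move a response rate visibly.

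Second, the study is meant to describe 400 mg weekly. A crossover patient's early events, exposure time and PK samples come from 200 mg. With no dose split, they can enter summaries that will be read as describing 400 mg.

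**Working it through.** **1. Populations side by side.** A completing patient has *n* injections of 200 mg followed by 13 − *n* of 400 mg.

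| *n* | SAF (10.3.1) | PP (10.3.1), if visits 1 and 13 assessed | 10.5.3 |
|---|---|---|---|
| 0 | in | in | in |
| 1 or 2 | in | in | in, pooled with all-400 mg |
| 3 to 12 | in | in | out |

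The conflict is confined to the last row.

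**2. What the grouping terms can mean.** Groups A and B differ by anti-TNF history, and both are described as receiving 400 mg (synopsis, 2.5). If the terms mean Groups A and B, every crossover patient has a group, but no dose split is planned. If they mean dose, no rule places a patient who received both. Section 4.1 describes the 200 mg injections as received in this study, so the first dose of study drug is naturally the first 200 mg injection.

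**3. Dose and time per crossover patient.** Cumulative dose = 200*n* + 400(13 − *n*) mg, against 13 × 400 = 5,200 mg. The 10.5.5 formula gives (84 − 0) + 7 = 91 days for every completer on the nominal calendar, of which 7*n* days are on 200 mg.

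| *n* | Share of 13 injections | Cumulative dose | Share of 5,200 mg | Days on 200 mg, of 91 |
|---|---|---|---|---|
| 2 | 15.4% | 4,800 mg | 92.3% | 14 |
| 4 | 30.8% | 4,400 mg | 84.6% | 28 |
| 8 | 61.5% | 3,600 mg | 69.2% | 56 |
| 12 | 92.3% | 2,800 mg | 53.8% | 84 |

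**4. Pre-dose PK.** Section 6.1 samples before dosing at visits 3, 5, 9 and 13 (days 14, 28, 56, 84). The documents give no half-life and do not state linearity, so assume linear one-compartment PK, rapid absorption and a half-life of 7 to 28 days. Let *r* be the fraction remaining after one week. A dose given *j* weeks earlier contributes in proportion to *r*^*j*. The ratio to an all-400 mg patient is 1 − 0.5 × (sum of *r*^*j* over the 200 mg doses) / (sum of *r*^*j* over all doses so far). For example, with *n* = 2, day 28 and *r* = 0.5: 1 − 0.5 × (0.125 + 0.0625)/0.9375 = 90%.

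| *n* | Visit 3 | Visit 5 | Visit 9 | Visit 13 |
|---|---|---|---|---|
| 2 | 50% | 79–90% | 93–99% | 97–100% |
| 4 | 50% | 50% | 83–97% | 93–100% |
| 8 | 50% | 50% | 50% | 79–97% |
| 12 | 50% | 50% | 50% | 50% |

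If the 10.5.3 limit governs PK, *n* = 2 is the largest case; if not, the lower rows also apply. At visit 3, let *m* of 20 patients sit at 0.5 and the rest at 1. The mean is 1 − 0.5*m*/20 and the SD is √[(20/19)(*m*/20)(1 − *m*/20) × 0.25]. For *m* = 1, 2, 4 the mean is 97.5%, 95%, 90% of the all-400 mg mean, and dose mixing alone gives a CV of 11.5%, 16.2%, 22.8%.

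**5. HiSCR illustration.** Assume 20 patients including the crossover patients (the plan does not say whether they count within the 20), 12 responders, and *m* patients over the limit. The plan names no interval method; exact (Clopper-Pearson) intervals are used. The ends of the 10.5.3 range correspond to all *m* excluded patients being responders (low) or non-responders (high).

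- 10.3.1: 12/20 = 60.0% (36.1 to 80.9).
- 10.5.3, *m* = 1: 11/19 = 57.9% (33.5 to 79.7) to 12/19 = 63.2% (38.4 to 83.7).
- 10.5.3, *m* = 2: 10/18 = 55.6% (30.8 to 78.5) to 12/18 = 66.7% (41.0 to 86.7).
- 10.5.3, *m* = 4: 8/16 = 50.0% (24.7 to 75.3) to 12/16 = 75.0% (47.6 to 92.7).

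**The case against.** The best defence is that 10.3.1 gives the general sets and 10.5.3 the specific exclusion. The limit stands under a heading for secondary endpoints and speaks of the data analysis generally, not of HiSCR alone. This largely stands: it is the natural reading for the clinical secondary endpoints. What remains is that neither section says so, and that PK, though a secondary endpoint, is analysed elsewhere without the limit.

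A reader might infer that crossover patients have no place in the safety tables. The documents do not support that. Sections 3, 8.2, 10.5.2.1 and 10.5.2.2 make it plausible that cohort and treatment group mean Groups A and B, and then every patient has a group. But that same reading means no dose split is planned.

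A reader might also infer that the plan necessarily mixes doses. That is too strong while the grouping terms are undefined; the supportable statement is that 200 mg data can enter these summaries. The dose-number and dose-volume summary in 10.5.5 helps in part, but it does not divide events or time by dose, and the documents do not describe how the 200 mg dose was presented, so volume may or may not reveal it.

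Finally, the sample is one of convenience, the primary endpoint has no formal test (10.1, 10.2), and Section 10 is the basis for an SAP that may be revised. This limits the consequence and makes the correction easy.

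**Conclusion.** The point holds and should be fixed. Two stated rules give different secondary-endpoint populations for patients with three or more 200 mg injections. Separately, the safety, exposure and PK rules do not separate 200 mg from 400 mg data, although the primary objective concerns 400 mg.

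The overall effect cannot be sized because the number of crossover patients is not given; with none, it is nil. Per patient, the dose and time figures are arithmetic on the nominal schedule. The PK figures rest on assumed linearity and half-life, and the HiSCR figures on an assumed response rate and crossover count; *n* = 12 is a theoretical extreme.

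A reader might infer that the efficacy conclusions or an error rate are compromised. The documents do not support that: the analyses are descriptive, so what is affected is which patients and which dose each summary describes.

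**What to change.** 1. In 10.3.1, name a separate efficacy set that applies the sponsor's own limit of two 200 mg injections to both the SAF-based and the PP analyses of the clinical secondary endpoints. Refer to it in 10.5.3. Leave the safety SAF unchanged. A HiSCR table for patients treated only with 400 mg is optional.
2. Keep all treated patients in the safety analysis and define *treatment dose cohort*. For patients given both doses, tabulate treatment-emergent events by dose at onset and exposure by dose received, showing the 200 mg period separately. Add a note that carry-over makes attribution after the switch approximate.
3. In 10.5.4, summarise PK by visit and dose received.

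The cost is SAP wording and a few split tables. No new data are needed, because injection and event dates are already recorded. The downside is that fewer patient-weeks are credited to 400 mg, by an amount that depends on the unstated number of crossover patients. No change to any dose or crossover rule is proposed.
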